12.7. Definition of End of Trial

The end of the trial is defined as the date of last participant 6 month follow-up.

13. PARTICIPANT SAFETY

13.1. Definitions

Term	Definition		
Adverse Event (AE)	 adverse event is; any unintentional, unfavourable clinical sign or symptom any new illness or disease or the deterioration of existing disease or illness 		
Serious Adverse Event (SAE)	 A serious adverse event is any untoward medical occurrence that: results in death is life-threatening requires inpatient hospitalisation or prolongation of existing hospitalisation results in persistent or significant disability/incapacity consists of a congenital anomaly or birth defect Other 'important medical events' may also be considered serious if they jeopardise the participant or require an intervention to prevent one of the above consequences. NOTE: The term "life-threatening" in the definition of "serious" refers to an event in which the participant was at risk of death at the time of the event; it does not refer to an event which hypothetically might have caused death if it were more severe. 		
Related Unexpected Serious Adverse Event (RUSAE)	 The National Research Ethics Service (NRES) defines related and unexpected SAEs as follows: 'Related' – that is, it resulted from administration of any research procedures; and 'Unexpected' – that is, the type of event is not listed in the protocol as an expected occurrence. 		

13.2. Expected Adverse Events/ Serious Adverse Events (non-reportable)

In recognition of this, events fulfilling the definition of an AE or SAE will not be reportable in this study unless they are specified in the section below or fulfil the definition of a Related and Unexpected Serious Adverse Event (RUSAE).

13.3. Expected serious adverse events – standard reporting

The following events are expected within the study population and will be collected from date of consent until six months post-registration:

- Hospital admissions and re-admissions
- Life-threatening repeated self-harm not leading to hospital admission
- Death (including Suicide)

Deaths

With a sample this small we would not *expect* any deaths; however the expected rate of deaths for those who self-harm is approximately 60-100 times that of the population as a whole, thus it is possible that some people may die as a consequence of self-harm during the course of the study. Additionally there may be deaths due to other causes within the study population.

All deaths occurring from the date of consent up to six months post-registration must be recorded on the Death Form and faxed to the CTRU **within 24 hours** of staff or researchers becoming aware of the event. The original form should also be posted to the CTRU in real time and a copy retained at site.

Reports will be reviewed by the Chief Investigator within one working day of receipt by CTRU. The Programme Steering Committee (PSC), Funder and Sponsor will be informed of the death within one month of reporting by site.

It is possible that families and / or coroners may wish to speak to someone representing the trial about trial participant deaths, as well as to local Mental Health Service staff who have provided treatment. The Chief Investigator would be available for such meetings if required.

As deaths are more likely within this population they will not be subject to expedited reporting to the main REC, unless the PSC advises that the frequency of self-harm related and / or all deaths observed within the trial population is significantly higher than that expected in the general self-harm population.

Hospital admissions and re-admissions

Hospital attendance details will be obtained by researcher review of local hospital records and participant self-report, and monitored on a regular basis by the PMG and PSC. Any safety concerns identified by the PSC must be reported to Main REC and the Sponsor by CTRU within 15 days of identification, and appropriate action taken.

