5. BACKGROUND

5.1. Nature of the problem

Self-harm is a major public health challenge with estimated lifetime prevalence of 5-6% (1) and some 220,000 hospital attendances annually in England and Wales (2). Repetition of self-harm is common with 70% of hospital attenders reporting previous episodes of self-harm (3). Up to 20% of those who present to hospital give a history of over five acts (3) and about 25% attend hospital for a subsequent act during 18 month follow-up (3). For those seen in hospital after an episode which represents at least their third attendance, more than 50% will go on to a further repeat attendance (4). We know most about hospital attendance because of ease of data collection, but it is apparent that many additional episodes do not lead to hospital attendance (5, 6). A reasonable assumption is therefore that some 40-50,000 hospital attendances a year are accounted for by those who repeatedly self-harm, with as many episodes again not leading to hospital attendance (7).

Repeated self-harm especially is associated with other problems such as depression and misuse of alcohol, with poor quality of life and with problems with interpersonal and social function (8): the risk of suicide is higher in the presence of a history of repeated episodes (9). Multiple repetition bears a significant cost both to the individual and the healthcare system; total healthcare costs rise significantly in the six month period following hospital attendance if the episode is number five or greater compared to a first episode (10).

An intervention that improves the quality of life of people who repeatedly self-harm and that could be delivered without the need for expensive specialist services would be of potential benefit to tens of thousands of those who attend hospital each year. In addition to the personal and social benefits, a reduction in hospital attendance would be of benefit to the health service (local estimates are that each ED attendance and assessment costs £12-1400) and a reduction in primary care attendance would reduce burden on GPs who have little specific to offer.

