17. STATISTICAL CONSIDERATIONS

17.1. Sample size:

We plan to recruit 30 participants to provide sufficient data to assess progression criteria to inform the decision to move to a definitive randomised Phase III evaluation (WP4). As this study is designed to determine the feasibility of a confirmatory trial and not to assess proof of concept or evaluate effectiveness, formal power calculations are not appropriate

Progression criteria will assess recruitment, follow-up, delivery and acceptability of the intervention using a traffic light system (Table 2). With 30 participants, the 95% CI around our green (go) criteria will exclude values in the red zone, relating to our stopping criteria. Therefore, with 30 patients, should we meet the go criteria we can be sufficiently confident that follow-up, delivery and acceptability will not fall to unacceptable levels as defined by the red (stop) criteria.

Recruitment of 30 participants will take place over four months in four centres, with approximately two to three participants recruited per month per center. With at least two therapists per center, this corresponds to one to two new participants a month per therapist, in line with recruitment and capacity requirements for the planned definitive trial (WP4).

Table 2 Feasibility study progression criteria

	Red	Amber	Green
			(95% CI)
Recruitment : Average no. patients	<4	4-7	>7
recruited / month			

Follow-up: % patients completing	<60%	60-75%	>75%
6m primary outcome			(95% Cl: 59.5%, 90.5%)
Delivery: % therapist delivering	<60%	60-80%	>80%
key intervention components			(95% Cl: 65.7%, 94.3%)
(overall and by each therapy)			
Acceptability: % participants	<50%	50-70%	>70%
attending 1st session			(95% CI: 53.6%, 86.4%)

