18.1. Programme Steering Committee (PSC)

The PSC will provide overall supervision of the study - in particular, study progress, adherence to protocol, participant safety, and consideration of new information. The committee will meet once during the set-up period and at least annually thereafter for the duration of the study. A subcommittee of the PSC will be convened where necessary to monitor safety data.

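### Listing death as an expected event takes even a research-related death off the RUSAE route, and the expedited trigger left for deaths is a frequency comparison that 30 participants can hardly inform

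*Protocol*

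**What the plan says.** Section 13.3 of the protocol lists death, including suicide, among the expected serious events that "will be collected from date of consent until six months post-registration". The paragraph on deaths adds three things:

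- In so small a sample no deaths would be expected, although "the expected rate of deaths for those who self-harm is approximately 60-100 times that of the population as a whole".
- Sites report a death to the CTRU within 24 hours, and the Chief Investigator reviews the report within one working day of receipt. After that, "The Programme Steering Committee (PSC), Funder and Sponsor will be informed of the death within one month of reporting by site".
- Deaths are exempt from expedited reporting to the main REC unless the PSC advises that the frequency of self-harm-related deaths, or of all deaths, "is significantly higher than that expected in the general self-harm population".

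Section 13.1 defines an unexpected event as one whose type the protocol does not list as expected. Section 13.4 gives related and unexpected SAEs a faster path: Chief Investigator review, Sponsor notice within one working day, and a report to the main REC within 15 days.

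Two further provisions bear on the point. Under hospital admissions, section 13.3 has admissions "monitored on a regular basis by the PMG and PSC", and then requires any safety concern that the PSC identifies to go to the REC and Sponsor within 15 days of identification. Section 18.1 says of the PSC: "The committee will meet once during the set-up period and at least annually thereafter for the duration of the study". It also allows a PSC subcommittee to be convened, where necessary, to look at safety data.

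**The concern.** Read together, sections 13.1, 13.3 and 13.4 give the gravest outcome a slower path than a lesser one. A related SAE of an unlisted type reaches the Sponsor in one working day and the REC in 15 days. A death judged related to the same research procedures may take a month to reach the Sponsor. Its expedited route to the REC depends on a comparison of frequencies, not on what happened to that participant. For deaths, no assessment of relatedness is stated at all.

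At stake is whether the first death in a study of newly modified therapies, in people at raised risk of suicide, gets a prompt independent look while others are still being registered. A frequency rule cannot provide that if one death seldom meets it.

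The section also calls death both a listed expected event and something not to be expected in this sample, so the PSC has no clear starting point for its judgement.

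**Working it through.** The protocol gives no expected number of deaths, threshold count or significance level for this rule, so there is no figure of its own to reproduce.

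**Inputs from the protocol**
- Sample size and pace (section 17.1): "Recruitment of 30 participants will take place over four months in four centres".
- Observation: about six months per participant (section 13.3).
- Multiplier on the population death rate: 60 to 100 (section 13.3).

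**Assumptions, not in the protocol**
- Population death rate to which the multiplier applies: 10 per 100,000 per year, range 5 to 20.
- The rule is read as a one-sided 5% test.

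**Exposure.** 30 × 0.5 = 15 person-years.

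**When one death is enough.** With annual reference rate r, P(at least 1 death) = 1 − exp(−15r). This is below 0.05 when r < −ln(0.95)/15 = 0.0513/15 = 0.00342, or about 0.34% per year. Dividing by the multiplier gives a population rate below 5.7 per 100,000 (×60) or 3.4 per 100,000 (×100). At a one-sided 2.5% level the limit falls to about 0.17% per year.

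**How many deaths are needed.** Six-month risk p = 1 − exp(−0.5r), then the exact binomial upper tail with n = 30:

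| Population rate per 100,000 | Multiplier | r per year | Expected deaths | P(≥1) | P(≥2) | Deaths needed at 5% |
|---|---|---|---|---|---|---|
| 5 | 60 | 0.30% | 0.045 | 0.044 | 0.001 | 1 |
| 5 | 100 | 0.50% | 0.075 | 0.072 | 0.003 | 2 |
| 10 | 60 | 0.60% | 0.090 | 0.086 | 0.004 | 2 |
| 10 | 100 | 1.00% | 0.150 | 0.139 | 0.010 | 2 |
| 20 | 60 | 1.20% | 0.180 | 0.165 | 0.014 | 2 |
| 20 | 100 | 2.00% | 0.300 | 0.259 | 0.036 | 2 |

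Below this range, at 2 per 100,000, P(≥1) is 0.018 to 0.030 and one death would be enough.

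**Ability to detect an excess.** Suppose two deaths are needed and the reference rate is 0.6% to 1.0% per year. A true rate five times the reference gives two or more deaths with probability 0.07 to 0.17. A true rate ten times the reference does so with probability 0.22 to 0.43.

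**Registrations during the notice period.** 30/4 = 7.5 per month. A one-month wait during recruitment therefore spans 7 to 8 registrations, and 7.5/30 = 25% of the sample.

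**The case against.** The strongest reply is that the rule is a committee judgement and not a hypothesis test. Section 17.3.2 says the study reports estimates and intervals instead of testing, and a PSC told that no deaths were expected could treat a single one as an excess. This stands in part: the 5% level and the base rates are assumptions made here. It does not rescue the rule, because the stated criterion is still a frequency set against a reference that the protocol does not quantify, and 15 person-years say little about frequency on any reading.

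Section 13.4 also leaves responsibilities to a guidance document, and section 18 leaves monitoring to a Monitoring Plan. Those may add detail, but they would have to work around the definitions that section 13 itself fixes.

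A reader might infer more than the text supports:

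- *That this is the only way a death can reach the REC.* It is not. The exemption concerns expedited reporting, and the sentence on any PSC safety concern carries no significance condition. However, that sentence sits under hospital admissions, and its 15 days start only when the PSC identifies a concern.
- *That the PSC meets too late to act.* Recruitment plus follow-up is 4 + 6 = 10 months, so annual meetings alone could miss it, but only if the previous meeting fell within about two months before first registration. Annual is a minimum, a subcommittee is available, and notice of a death does not wait for a meeting. What remains is that no death is named as a trigger for the subcommittee.
- *That the comparator makes the trigger harder to meet.* Section 5.1 says "the risk of suicide is higher in the presence of a history of repeated episodes", so the general self-harm population is not a close match for this sample. But a benchmark of repeat self-harm would raise the expected count and make one death less likely to meet the rule.
- *That three or more deaths would be needed if all causes count.* This applies the multiplier to an all-cause base rate. The protocol does not say that it belongs there: section 13.3 uses it when discussing death from self-harm and mentions other causes separately.

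The Chief Investigator's review is prompt, but it is not independent, and no onward step is stated beyond the one-month notice.

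**Conclusion.** The point holds as a gap between sections 13.1, 13.3, 13.4 and 18.1. That a death cannot be a RUSAE follows from the protocol's own definitions and needs no assumption, as does the contrast between one working day and up to one month for Sponsor notice.

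The size of the threshold problem is conditional. On a one-sided 5% reading, one death is enough only below about 0.34% per year. Over the assumed range of 5 to 20 per 100,000 with multipliers of 60 and 100, two deaths are needed in five of the six cases. If the true base rate were lower, one death could suffice.

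The figure of 7 to 8 registrations is an outer limit: it applies to a death reported with at least a month of recruitment left and the full month used. The provisions on PSC safety concerns and the subcommittee soften the gap without closing it. The documents do not show that deaths go unreported or that the PSC is unable to act.

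**What to change.** Reconcile sections 13.1, 13.3, 13.4 and 18.1 as follows:

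1. State that every death receives an individual review of relatedness to the research procedures, although death is a listed event.
2. Notify the PSC chair (or safety subcommittee) and the Sponsor on the one-working-day clock already used for RUSAEs.
3. Have the PSC advise on REC reporting case by case within 15 days, in place of the frequency comparison.
4. Name any death as a trigger for the PSC safety subcommittee.
5. State that the requirement to pass PSC safety concerns to the REC covers deaths as well as admissions.
6. Resolve whether death is to be called expected in this sample.

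Neither a new benchmark population nor a fixed calendar of PSC meetings is needed. The cost is amendment wording and, for each death, a short remote review by a committee that already exists.

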13.4. Related and Unexpected SAEs – expedited reporting

All Related/Unexpected SAEs occurring from the date of consent up to six months post registration must be recorded on the Related/Unexpected Serious Adverse Event (RUSAE) Form and faxed to the CI within 24 hours of the clinical research staff becoming aware of the event.

For each Related/Unexpected SAE the following information will be collected:

- date of SAE
- full details in medical terms with a diagnosis, if possible
- its duration (start and end dates; times, if applicable)
- action taken
- outcome

Any follow-up information should be communicated with the CI as soon as it is available. Events will be followed up until the event has resolved or a final outcome has been reached. The original RUSAE Form(s) should be retained by site until the event has reached a final outcome and all queries have been resolved.

All Related / Unexpected SAEs will be reviewed by the Chief Investigator, notified to the sponsor within one working day, and are subject to expedited reporting to the main REC by the CTRU on behalf of the Chief Investigator within 15 days.

Responsibilities of the Chief Investigator, CTRU, PSC and Sponsor will be detailed in a study specific guidance document

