11. INTERVENTION DETAILS

11.1. Intervention Delivery

Recruited participants will receive up to 12 sessions of the intervention over a maximum of 6 months; with an additional option of 1-2 booster sessions (typically by telephone) within 3 months of completion of therapy. Sessions will commence as soon as possible following entry in to the trial. The intervention will be delivered in accordance with guidance notes developed for each of the modified therapies, and will be undertaken at appropriate Trust premises.

Sessions may be delivered face to face, via telephone or video call, will last for 45 to 50 minutes in duration and will occur where possible on a weekly basis. Mode of delivery will be determined by current Trust practice, therapist preference and participant preference. All sessions will be audio-recorded for use in supervision and independent fidelity assessment. Where sessions are delivered via video calling only audio will be recorded.

Rules for non-attendance are in line with practice from similar RCT for this patient group (for example DBT trials). Participants will be allowed a maximum of four appointments for which they fail to attend or cancel at the last minute.

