- Admissions to / attendance at hospital for other			
reasons			х
	Ongoing co	ollection at the	rapy sessions
- Repeat of self-harm (T)	and monthly text messages		essages
- Serious adverse event reporting	Ongoing collection		ion
- Details of further self-harm episodes since consent			
(collected via 2-way SMS from Participant)		х	х
Questionnaires (Researcher admin at baseline, CTRU			
postal admin at 6 months)			
- Clinical Outcomes in Routine Evaluation - Outcome			
Measure (CORE-OM)	Х		Х
- Hopelessness - Beck Hopelessness Scale	Х		Х
- Depression PHQ 9	Х		Х
- Social connectedness – The Social Connectedness			
Scale - Revised	Х		Х

Self-reported episodes of self-harm		Х	
- Self-reported resource use	Х	Х	
Qualitative Interview Study (R & P interview at 6			
months – n=18))			
- Acceptability and perceived burden of questionnaire			
completion		Х	
- Details of treatment received and views on this		Х	
P = Participant, R = Researcher, T = Therapist			

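### At the permitted maximum, booster contact can run to about month 9, but the recording of SAEs, deaths and RUSAEs is dated only to six months post-registration

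*Protocol*

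**What the plan says.** **Intervention schedule.** Section 11.1 sets the main course of therapy: "Recruited participants will receive up to 12 sessions of the intervention over a maximum of 6 months". After that course has ended, the same section permits further contact, described as coming "with an additional option of 1-2 booster sessions (typically by telephone) within 3 months of completion of therapy". Sessions are to start as soon as possible and to be weekly where possible. Up to four missed or late-cancelled appointments are tolerated. No maximum start delay is given. The flow chart in section 3 places two booster contacts in the intervention box.

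**Safety recording.**
- Section 13.2 makes adverse and serious adverse events non-reportable "unless they are specified in the section below or fulfil the definition of a Related and Unexpected Serious Adverse Event (RUSAE").
- Section 13.3, on expected serious events (admissions, life-threatening self-harm without admission, deaths): "The following events are expected within the study population and will be collected from date of consent until six months post-registration".
- Section 13.3, on deaths: "All deaths occurring from the date of consent up to six months post-registration must be recorded on the Death Form".
- Section 13.4, on RUSAEs: "All Related/Unexpected SAEs occurring from the date of consent up to six months post registration must be recorded". A later sentence in that section has no date: "All Related / Unexpected SAEs will be reviewed by the Chief Investigator, notified to the sponsor within one working day", followed by reporting to the ethics committee.

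**Related text.** Section 12 describes the 6-month follow-up as matching the time by which therapy and any boosters are expected to be complete. Table 1 has a row, "Serious adverse event reporting", marked as ongoing. Section 12.7 ends the trial at the last participant's 6-month follow-up.

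**The concern.** Boosters belong to the trial intervention, and section 15 counts their uptake as a delivery outcome. Recording of serious events would normally cover all contact that the trial itself delivers. Here the schedule is limited by two successive maxima (6 months, then 3 months), while the recording window has one fixed end date at six months post-registration. A participant who finishes therapy late can therefore receive a permitted booster after the dated window has closed.

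The consequence differs by type of event:
- **Deaths and hospital admissions:** the dated text does not require them to be recorded.
- **Life-threatening self-harm without admission:** it need not go through SAE reporting. Table 1 and section 12.3 do have therapists record repeat self-harm at sessions, so there is a data route, but not the safety route.
- **RUSAEs:** the duty is unclear. The recording sentence is dated; the exception in 13.2 and the review and notification sentence in 13.4 are not.

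The population gives this some weight: section 13.3 puts mortality after self-harm at roughly 60 to 100 times that of the general population.

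**Working it through.** The protocol gives no figure to reproduce; the check is timeline arithmetic.

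**Inputs from the protocol**
- Main therapy: at most 6 months, weekly where possible, up to 12 sessions (11.1).
- Boosters: up to 3 months after completion (11.1).
- Recording window: ends 6 months after registration (13.3, 13.4).

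**Conversion.** One month = 365.25 / 12 / 7 = 4.348 weeks, so 6 months = 26.1 weeks and 3 months = 13.0 weeks.

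**Formula.** Let T be the week after registration in which therapy is completed and b the weeks from completion to the last booster (0 to 13.0).

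Weeks outside the window = max(0, T + b − 26.1)

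**Assumptions.** Therapy starts at registration, which favours the protocol. T = 20 and b = 4, 6 and 8 are illustrative values inside the permitted range.

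| Case | T | b | T + b | Weeks outside |
|---|---|---|---|---|
| 12 weekly sessions, no gaps | 11 | 13.0 | 24.0 | 0 |
| Four missed weeks, all made up (assumed) | 15 | 13.0 | 28.0 | 1.9 |
| Slower delivery | 20 | 6 | 26.0 | 0 |
| Slower delivery | 20 | 8 | 28.0 | 1.9 |
| Slower delivery | 20 | 13.0 | 33.0 | 6.9 |
| Permitted maximum | 26.1 | 4 | 30.1 | 4.0 |
| Permitted maximum | 26.1 | 8 | 34.1 | 8.0 |
| Permitted maximum | 26.1 | 13.0 | 39.1 | 13.0 |

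**Latest completion that keeps the last booster inside the window:** T = 26.1 − b, which is week 22.1, 20.1 or 18.1 for b = 4, 6 or 8, and about week 13 for a booster on the last permitted day. Against prompt completion at week 11, the slack is 11.1, 9.1, 7.1 and about 2 weeks.

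**Start delay.** Section 11.1 does not say whether its 6-month maximum runs from registration or from the first session. With an assumed 4-week delay and uninterrupted weekly sessions, the last permitted booster day is week 4 + 11 + 13.0 = 28.0, or 1.9 weeks outside. If the maximum runs from the first session, an assumed delay of 2 to 8 weeks moves the outer limit from month 9 to months 9.5 to 10.8.

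**Does other text close the gap?** Section 12 states an expectation and sets no limit on booster dates. The Table 1 row has no end date, and the table's last column is 6 months, so it cannot override the explicit dates in 13.3 and 13.4. No other section extends the window.

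**The case against.** The strongest reply is that month 9 arises only by adding two maxima. At the intended pace the whole booster window closes at about week 24. Even with four missed weeks made up, a booster up to about 11 weeks after completion is still inside. Section 12 shows that the authors considered the alignment and expected boosters to be finished by the 6-month follow-up. Boosters are optional, few and typically by telephone, and the clinical risk management in section 11.5.2 has no date limit. All of this stands and keeps the point minor. It does not remove it, because an expectation about timing does not restrict what 11.1 permits.

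A reader might infer more than the text supports:
- *That the trial routinely delivers contact to month 9.* It does not; that is the outer limit.
- *That sections 11.1 and 12 contradict each other.* An expected course can sit alongside a longer maximum.
- *That late self-harm goes unrecorded.* Therapists' recording of repeat self-harm at sessions is not dated to six months.
- *That a late RUSAE need not be reported.* The undated sentences in 13.2 and 13.4 point the other way, so the duty is ambiguous rather than absent. Section 13.4 also refers responsibilities to a study-specific guidance document that is not available here; it may help staff, but the window itself is fixed in the protocol.

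**Conclusion.** The point holds as a minor gap in the safety text. Between 0 weeks (prompt weekly delivery) and about 13 weeks (permitted maximum) of allowed booster contact lies outside the dated recording window, taking therapy to start at registration; a start delay can only reduce the slack. Deaths and admissions in that interval are the clearest omission. How many of the 30 participants would be affected cannot be derived from the protocol, and it could be none. The sample size, the Table 2 progression criteria and the 6-month CORE-OM are unaffected.

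**What to change.** In sections 13.3 and 13.4, run the recording of expected SAEs, deaths and RUSAEs from consent to the later of six months post-registration and the participant's last trial therapy or booster contact. Align the end-of-trial definition in 12.7, and note in section 12 that boosters may fall after the 6-month follow-up. Leave the 6-month questionnaire time point unchanged.

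The cost is a short wording amendment to four sections. Reporting forms stay open up to about 3 months longer for some participants (longer only if a delayed start extends the therapy maximum), with no new assessments.

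The alternative is one line in 11.1 requiring boosters to finish by six months post-registration. That is simpler, but it shortens the booster window for late finishers and removes it for anyone completing therapy at the 6-month limit. It changes the intervention rather than the recording, so the first option is preferable.
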